10.3	PHASE 2 - SECONDARY OUTCOME MEASURE – PROGRESSION FREE SURVIVAL.....	54
10.3.1	Relevant Subset	55

10.3.2 Progression-free Survival Definition	55
10.3.3 Measurement Methods	55
10.3.4 Measurement Time Points	55
10.4 PHASE 2 - SECONDARY OUTCOME MEASURE – INDUCTION OF TUMOR-SPECIFIC IMMUNE RESPONSES	55
10.4.1 Relevant Subset	55
10.4.2 Tumor-specific Immune Response Definition	55
10.4.3 Measurement Methods	55
10.4.4 Measurement Time Points	55
11. REGULATORY CONSIDERATIONS	56
11.1 INSTITUTIONAL REVIEW OF PROTOCOL.....	56
11.2 DATA AND SAFETY MONITORING PLAN.....	56
11.3 DATA MANAGEMENT PLAN	56
11.4 CONFIDENTIALITY	56
12. STATISTICAL CONSIDERATIONS	57
12.1 STATISTICAL DESIGN	57
12.2 PRIMARY ANALYSIS.....	57
12.2.1 Analysis Population	57
12.2.2 Analysis Plan	57
12.3 SAMPLE SIZE.....	57
12.3.1 Accrual estimates	57
12.3.2 Sample size justification	57
12.3.3 Effect size justification	58
12.4 CRITERIA FOR FUTURE STUDIES	58
13. REFERENCES	59
APPENDICES	62
APPENDIX A: PARTICIPANT ELIGIBILITY CHECKLIST	62
APPENDIX B: DEFINITION OF TUMOR RESPONSE USING IRRC	66
APPENDIX C: ECOG PERFORMANCE STATUS	68
APPENDIX D: LIST OF P450 INHIBITORS AND INDUCERS	69
APPENDIX E: CONTRACEPTION GUIDELINES	?

[figure not shown]
PROTOCOL SYNOPSIS

TITLE	Intratumoral Injection of SD-101, an Immunostimulatory CpG, in combination with Ibrutinib and Local Radiation in Relapsed or Refractory Low-Grade Follicular Lymphoma
STUDY PHASE	Phase 1b/2
INDICATION	Relapsed/Refractory Low grade Follicular Lymphoma, Mantle cell Lymphoma, Marginal Zone Lymphoma
INVESTIGATIONAL PRODUCT OR PROCEDURE	Intratumoral SD-101 plus low-dose local radiotherapy plus oral ibrutinib
PRIMARY OBJECTIVE(S)	
Phase 1b:
 
1) To determine the recommended phase 2 dose (RP2D) of intratumoral SD-101 in combination with ibrutinib and radiation in subjects with relapsed or refractory B-cell lymphoma2) To determine the safety and tolerability of SD-101 in combination with ibrutinib and radiation in subjects with relapsed or refractory B-cell lymphoma 
Phase 2:
 
1) To evaluate the efficacy of intratumoral SD-101 in combination with ibrutinib and radiation in subjects with relapsed or refractory B-cell lymphoma by assessing overall response rate
SECONDARY OBJECTIVE(S)	
Phase 2:
 
1) To evaluate progression-free survival after treatment with intratumoral SD-101 in combination with ibrutinib and radiation in subjects with relapsed or refractory B-cell lymphoma2) To evaluate the induction of tumor-specific immune responses by treatment with intratumoral SD-101 in combination with ibrutinib and radiation in patients with relapsed or refractory B-cell lymphoma

TREATMENT SUMMARY	
Local low-dose radiation therapy to a single site of disease combined with intratumoral injections to the same single site.
 
SD-101 (CpG) – Intratumoral injection on Day 2, then once every week x 4 successive weeks for a total of 5 injections at a dose of 3 mg per dose in cohort 1 or 1 mg per dose in cohort -1.
 
Ibrutinib orally at a dose of 560 mg daily starting on Day 10 until progression of disease or for 96 weeks, whichever comes first.
 
In the safety portion of the study, a starting dose of 3 mg SD-101 and 560 mg ibrutinib will be studied and will follow a 6+3 dose de-escalation design. In the first cohort of 6 subjects, if ≤ 1 subjects experiences a DLT, then that dose level will be chosen as the recommended phase 2 dose. If 2 subjects experience a DLT, then an additional 3 subjects will be enrolled at the same dose level. If 3 or more of 6 to 9 subjects experience a DLT, dose de-escalation will occur with a new cohort of 6 subjects at a dose of 1 mg SD-101 and 560 mg ibrutinib.
 
Based on the data from dose de-escalation cohorts, a dose of SD-101 will be chosen and an additional cohort of 15 subjects will be treated at that dose in order to assess the clinical response rate.
 
Immune monitoring and follow-up will occur over the following 24 weeks.
 
Subjects without PD will be followed for immune and clinical response every 12 weeks until Week 96 or progression, whichever comes first.

SAMPLE SIZE	
This research study is looking for a total of up to 30 subjects with low-grade follicular lymphoma, marginal zone lymphoma, or mantle cell lymphoma. All subjects will be enrolled at Stanford University. A total of 6 to 15 subjects will be enrolled in the phase 1B 6 x 3 dose de-escalation portion. An additional 15 subjects will be enrolled in the expanded phase 2 cohort.
 
If ≤ 1 of 6 subjects experience a DLT at a dose of intratumoral SD-101 of 3 mg, we will proceed to the expansion phase. If 2 of 6 subjects experience a DLT at 3 mg, then an additional 3 subjects will be enrolled in the same dosing cohort. If ≥ 3 of 6 to 9 subjects

	experience a DLT, then a dose de-escalation cohort -1 of 6 subjects will be opened.
STATISTICAL CONSIDERATIONS	The sample size of 15 subjects in the expanded phase 2 cohort (with resulting total number of 21 to 24 subjects at the RP2D in the combined 1b/2 phases) allows estimation of the response rate +/- 0.21 with 90% confidence. The chance of obtaining three or fewer responses out of 15 is only 2.1% if the true response rate is 49%, with 49% ORR being a historical benchmark for response rate in this population.

SCHEMA

LIST OF ABBREVIATIONS AND DEFINITION OF TERMS

AE	Adverse event
BID	Twice daily
CBC	Complete blood count
CNS	Central nervous system
CpG	Cytosine-phosphate-Guanine
CRF	Case report/Record form
CR	Complete response
CTCAE	Common Terminology Criteria for Adverse Events
CTL	Cytotoxic T lymphocyte
DLT	Dose Limiting Toxicity
DSMB	Data Safety Monitoring Board
ECG	Electrocardiogram
GI	Gastrointestinal
Hgb	Hemoglobin
HIV	Human Immunodeficiency Virus
HPF	High-power field
HTN	Hypertension
IRB	Institutional Review Board
ISS	Immunostimulatory sequence
IV	Intravenous
LDH	Lactate dehydrogenase
LLN	Lower limit of normal
MTD	Maximum Tolerated Dose
ODN	Oligonucleotide
OS	Overall survival
PBL	Peripheral blood leukocytes
PLT	Platelet
PD	Progressive disease
PFS	Progression free survival
PQC	Product Quality Complaint
PR	Partial response
QD	Once daily
RECIST	Response evaluation criteria in solid tumors
RP2D	Recommended phase 2 dose
RR	Response rate
SAE	Serious adverse event
SD	Stable disease
SD-101	Immunostimulant CpG injection (Dynavax)
TTP	Time to progression
ULN	Upper limit of normal
UNK	Unknown
WBC	White blood cell
WHO	World Health Organization

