4. TREATMENT PLAN

4.1 Dose de-escalation Study Design

The study will use a 6+3 design with a goal of determining the recommended phase 2 dose. We will enroll a cohort of 6 subjects, with a 3 mg dose of intratumoral SD-101 and 560 mg dose of oral ibrutinib. The proposed initial dose of SD-101 is below the maximum tolerated dose as determined in previous trials, and there is extensive data regarding the safety of treatment with ibrutinib at the FDA-approved dose of 560 mg. Because no additional toxicity is anticipated with combination therapy of SD-101 and ibrutinib, the 6+3 dose de-escalation design will be employed, permitting rapid confirmation of the safety of the combination therapy and selection of the recommended phase 2 dose while still allowing detection of any unanticipated toxicity.

If 0 or 1 subjects out of the initial 6 subjects experience a DLT, we will chose this dosing as the recommended phase 2 dose level. If 2 out of 6 subjects experience a DLT, we will expand the

cohort and enroll an additional 3 subjects at the same dose level. If 3 out of 6-9 subjects in the initial dose cohort experience a DLT, then the dose de-escalation cohort -1 will accrue. This dose de-escalation cohort will be treated with 1 mg intratumoral SD-101 and 560 mg ibrutinib. If \leq 2 out of 6 subjects in the dose de-escalation cohort experience a DLT, then this dose will be considered the RP2D. If 3 or more subjects in the de-escalation cohort experience a DLT, the study will be stopped.

Table 1. Dose Escalation Plan

Cohort	Dose (mg)	Total Enrollment per Cohort	Dose Escalation Rules
-1	1 mg SD-101 560 mg ibrutinib	6	1 of 6 or 2 of 6 DLT, RP2D is established 3 of 6 DLT, trial is stopped
1	3 mg SD-101 560 mg ibrutinib	6-9	0 of 6 or 1 of 6 DLT, RP2D is established at this level 2 of 6 DLT, expand cohort to 9 subjects 2 of 9 DLT, RP2D is established at this level 3 of 6-9 DLT, decrease to dose level -1
Phase 2 Expansion	RP2D	15	If the incidence of study drug-related DLTs as defined previously equals or exceeds 33% of treated subjects at RP2D dose level 1, enrollment will be stopped for dose level 1, and enrollment of 15 subjects will begin at dose level -1. If the incidence of study drug-related DLTs equals or exceeds 33% of treated subjects at RP2D dose level -1, then the trial is stopped

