Phase 2 (SD-101 dose Cohort Expansion): Once the safety profile and tolerability of all doses tested has been characterized and the RP2D of SD-101 has been defined during the dose de-escalation phase of this trial, the RP2D dose cohort will be expanded by an additional 15 subjects. This will enable further characterization of the immunoregulatory activity and preliminary antitumor effects of this treatment regimen. The treatment schema for SD-101, RT and ibrutinib will remain the same as previously described.

Clinical safety monitoring of subjects enrolled during this additional Cohort Expansion portion of the study will be the same as conducted during the dose escalation portion of the study (ie, part 1). If the chosen RP2D is dose level 1 (3 mg SD-101) and the combined incidence of study drug-related DLTs of any kind (ie, Grade 3 injection site reaction, hematologic or non-hematologic DLT) is equal to or exceeds 33% of treated subjects at any point during treatment, this will prompt a halt in enrollment at that dose level. Enrollment of 15 subjects will then begin at the lower dose level of 1 mg SD-101. If the incidence of DLTs in the lower dose cohort equals or exceeds 33%, the trial will be stopped.

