12.3.2 Sample size justification

The reported overall response rate with single-agent ibrutinib in a similar population of relapsed/refractory low-grade follicular lymphoma has been 30% (12 of 40 subjects) (12), and

we previously reported an ORR of 27% to intratumoral CpG (4 of 15 subjects) (50). We will therefore expect overall response rate of >57% (ie, a 27% improvement over ibrutinib alone).

This trial design will enroll a minimum of 21 subjects at the recommended phase 2 dose (a minimum of 6 subjects in phase 1b and 15 subjects in the phase 2 expansion). For a true response rate of 57%, this sample size will provide 83.6% power to detect a significantly improved (95% confidence interval) response rate as compared to the previously reported ORR of 30% with ibrutinib alone.

A total of 6 to 15 subjects will be enrolled in the phase 1B 6 x 3 dose de-escalation portion. An additional 15 subjects will be enrolled in the expanded phase 2 cohort.

If $\leq 1/6$ subjects experience a DLT at a dose of intratumoral SD-101 of 3 mg, we will proceed to the expansion phase. If $2/6$ subjects experience a DLT at 3 mg, then an additional 3 subjects will be enrolled in the same dosing cohort. If ≥ 3 of 6 to 9 subjects experience a DLT, then a dose de-escalation cohort -1 of 6 subjects will be opened.

The sample size of 15 subjects in the expanded phase 2 cohort (with resulting total number of 21 to 24 subjects at the RP2D in the combined 1b/2 phases) allows estimation of the response rate $+\/- 0.21$ with 90% confidence. The chance of obtaining three or fewer responses out of 15 is only 2.1% if the true response rate is 49%, with 49% ORR being a historical benchmark for response rate in this population.

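### The sample-size text omits the phase 2 restart at 1 mg, under which total enrolment can reach 39 rather than 30 and the final dose has at most 15 subjects rather than at least 21

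*Combined protocol and SAP*

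**What the plan says.** The Protocol Synopsis (Sample Size) sets the ceiling: "This research study is looking for a total of up to 30 subjects". It builds this from two parts, repeated in Section 12.3.2: "A total of 6 to 15 subjects will be enrolled in the phase 1B 6 x 3 dose de-escalation portion" and "An additional 15 subjects will be enrolled in the expanded phase 2 cohort".

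Section 12.3.2 then gives the number at the RP2D: "This trial design will enroll a minimum of 21 subjects at the recommended phase 2 dose". From that it derives 83.6% power for a true response rate of 57% against 30%. The same section gives a range, "with resulting total number of 21 to 24 subjects at the RP2D in the combined 1b/2 phases", with a half-width of 0.21 at 90% confidence.

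Section 4.1 (text and Table 1) adds a rule for the expansion. If 3 mg is the RP2D and DLTs reach 33% of treated subjects, enrolment at 3 mg stops. "Enrollment of 15 subjects will then begin at the lower dose level of 1 mg SD-101". Table 1 then refers to the RP2D at dose level -1, and the trial stops if DLTs reach 33% there as well. The synopsis and Sections 12.3.1 and 12.3.2 do not mention this second group of 15.

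**The concern.** A ceiling and a minimum should hold on every path that the plan allows. Here the ceiling of 30 counts one expansion cohort, and the minimum of 21 assumes that a phase 1b cohort of at least six was treated at the dose finally taken forward. After a phase 2 halt neither assumption need hold.

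If the halt comes late, the site must either pass the stated ceiling or enrol fewer than the 15 written in Section 4.1, and no text says which governs. After any halt, early or late, the efficacy estimate at the final dose rests on fewer subjects than the power statement assumes.

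**Working it through.** **Inputs.** Phase 1b at 3 mg: 6 or 9 subjects (Table 1: "2 of 6 DLT, expand cohort to 9 subjects"). Phase 1b at 1 mg: 6 subjects, only if 3 mg fails in phase 1b. Expansion: 15. Restart after a phase 2 halt: 15 at 1 mg. Halt threshold: 33% (Section 4.1). Response rates: 30% and 57% (Section 12.3.2).

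**The plan's own figures.**
- Ceiling: 9 + 6 + 15 = 30.
- At the RP2D: 6 + 15 = 21 to 9 + 15 = 24.
- De-escalation inside phase 1b gives 6 + 15 = 21 at 1 mg, so that path agrees with the text.
- Power, normal approximation with the null variance in the critical value, one-sided 5%: Φ{[(p1 − p0)√n − 1.645√(p0(1 − p0))] / √(p1(1 − p1))}. At n = 21: (0.27 × 4.583 − 1.645 × 0.4583) / 0.4951 = 0.977, giving 83.6% as stated.
- Half-width at n = 15: 1.645 × √(0.25/15) = 0.212, the stated 0.21.

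**Maximum with the restart.** Table 1 allows 3 mg to go forward from nine subjects: "2 of 9 DLT, RP2D is established at this level". The boundary can then first be crossed at the 15th expansion subject:
- Pooled with phase 1b: 8/24 = 33.3%, after 7/23 = 30.4%.
- Expansion alone: 5/15 = 33.3%, after 4/14 = 28.6%.

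The total is 9 + 15 + 15 = 39. If the halt must fall before the 15th expansion subject enrols, it is 9 + 14 + 15 = 38. The total exceeds 30 exactly when more than 15 subjects were treated at 3 mg by the halt.

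**Number at the final dose.** Cohort -1 opens in phase 1b only when 3 mg fails there. On the phase 2 halt path nobody has yet received 1 mg, so the final dose has at most 15, and fewer if the 1 mg group itself stops.

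**How often.** The documents give no expected DLT rate, so the rates below are assumptions. Subjects are taken as independent, with the proportion checked after each expansion subject. The chance that 3 mg is selected is (1 − p)^6 + 6p(1 − p)^5 + 15p²(1 − p)^7. Section 4.1 does not say whether the 33% pools phase 1b, so both readings are shown. All figures are over all trials.

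| True DLT rate | 3 mg selected | Halt, pooled | Halt, expansion only | Total above 30, pooled | Total above 30, expansion only |
|---|---|---|---|---|---|
| 10% | 95.75% | 1.83% | 28.67% | 0.09% | 0.29% |
| 20% | 78.12% | 11.27% | 45.55% | 1.84% | 1.80% |
| 25% | 65.91% | 17.21% | 46.43% | 3.47% | 2.35% |
| 30% | 53.14% | 21.44% | 42.73% | 4.75% | 2.38% |

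The expansion-only figures are high because one DLT among the first three expansion subjects already meets 33%. A total of exactly 39 has probability 0.08% to 0.24% (pooled) at rates of 20% to 30%.

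**Power at 15.** Same formula: (0.27 × 3.873 − 1.645 × 0.4583) / 0.4951 = 0.590, giving 72.2%. Exact binomial: at least 8 of 15 gives 71.0% power at a one-sided level of 5.0%.

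**Timeline.** At 10 subjects per year (Section 12.3.1) plus 96 weeks (22.1 months), 30 subjects take 36.0 + 22.1 = 58.1 months, 32 take 38.4 + 22.1 = 60.5, and 39 take 46.8 + 22.1 = 68.9, against 60 in Section 3.5.

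**The case against.** The strongest case for the plan is that the branch is a contingency, that Section 4.1 expects no additional toxicity from the combination, and that most halts leave the ceiling intact. Much of this stands. With pooled counting at rates of 20%, 25% and 30%, only 16%, 20% and 22% of halts take the total above 30 (for example 1.84/11.27), and at a 10% rate a pooled halt is rare. It does not rescue the minimum of 21, which fails after every halt.

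Four stronger readings are tempting and are not supported:
- A reader might infer that precision fails too. The stated 0.21 is already the 15-subject value.
- A reader might set 51.5% power (at least 9 of 15) against 83.6%. That rule has a one-sided level of 1.5%, so the comparison changes the method and the level as well as the sample size.
- A reader might quote halt probabilities of 14%, 26% and 40%. These are conditional on 3 mg being selected and on pooled counting; over all trials they are 11%, 17% and 21%.
- A reader might say that the primary analysis must have only 15 subjects. Section 10.2.1 limits it to the RP2D, but Section 12.2.1 defines the response-evaluable population without a dose restriction. What fails is the count of 21, which Section 12.3.2 ties explicitly to the RP2D.

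**Conclusion.** The concern holds as a statement about bounds and power. The ceiling of 30 and the minimum of 21 are correct only if the phase 2 halt never occurs. With it, the ceiling is 39 in the worst case and the final dose has at most 15 subjects, whichever way the 33% is counted. Like-for-like power on that branch is about 72% rather than 83.6%, a loss of about 11 percentage points.

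How often this matters depends on a DLT rate that the documents do not give and on an unstated denominator: 11% to 21% of trials (pooled) or 43% to 46% (expansion only) at rates of 20% to 30%, and about 2% or 29% at 10%. Passing 30 is much less likely, about 2% to 5% at 20% to 30%. The timeline is at risk only on those late halts: the overrun is about half a month at 32 subjects, and 69 months belongs to the extreme of 39 alone.

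**What to change.** Reconcile the synopsis and Sections 12.3.1 and 12.3.2 with the halt rule in Section 4.1:

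- State the ceiling as up to 39 subjects, or state an explicit cap of 30 and the smaller restart cohort that follows (30 minus the number already treated at 3 mg, so as few as 30 − 24 = 6).
- Replace the minimum of 21 with 21 to 24 at the RP2D, or at most 15 if the expansion restarts at level -1.
- Add the power for that branch: about 72% at 15 subjects by the formula behind 83.6%. If the cap is chosen, give the lower power for smaller restart cohorts.
- Say whether the 33% counts phase 1b subjects, since the chance of the branch depends on it.

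The half-width needs no change. The cost is wording and a less favourable power figure; no subjects are added beyond those that Section 4.1 already allows. No change to the dose or the halt rule is proposed.

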1. OBJECTIVES

1.1. Primary Objectives

Phase 1b:

- 1) To determine the recommended phase 2 dose (RP2D) of intratumoral SD-101 in combination with ibrutinib and radiation in subjects with relapsed or refractory B cell lymphoma
- 2) To determine the safety and tolerability of SD-101 in combination with ibrutinib and radiation in subjects with relapsed or refractory B cell lymphoma

Phase 2:

- 1) To evaluate the efficacy of intratumoral SD-101 in combination with ibrutinib and radiation in subjects with relapsed or refractory B-cell lymphoma by assessing overall response rate

1.2. Secondary Objectives

Phase 2:

- 1) To evaluate progression-free survival after treatment with intratumoral SD-101 in combination with ibrutinib and radiation in subjects with relapsed or refractory B-cell lymphoma
- 2) To evaluate the induction of tumor-specific immune responses by treatment with intratumoral SD-101 in combination with ibrutinib and radiation in patients with relapsed or refractory B-cell lymphoma

2. BACKGROUND

2.1 Non-Hodgkin's lymphoma

Non-Hodgkin's lymphoma (NHL) is a group of histologically and biologically distinct lymphoid malignancies. 80 to 90% of NHLs are B-cell lymphomas, and the great majority of the rest are T-cell lymphomas. It is estimated that there will be 71,850 cases of NHL diagnosed in the US in 2015, representing 4% of all cancers diagnosed in the United States.(1) An estimated 19,790 deaths will result from NHL in 2015. Reporting from the US Surveillance, Epidemiology, and End Results (SEER) program indicates that the incidence of NHL has increased substantially in recent years, from 10.2 per 100,000 in 1973 to 18.5 in 1990, an increase of 81% overall and about 3.6% per year. The rapid increase in NHL incidence in the 1970s and 1980s has been surpassed only by the increases in lung cancer in women and malignant melanomas in both sexes.(2)

Non-Hodgkin's lymphomas encompass many histological types. The Revised European-American Classification of Lymphoid Neoplasms (REAL) developed in 1994 is the currently accepted classification. This was further refined by the World Health Organization (WHO) classification of hematologic malignancies in 1997. Based on this classification, NHLs are grouped into indolent (low-grade), aggressive and highly aggressive lymphomas based on the clinical behavior of each entity. Low-grade lymphomas (indolent lymphomas) can be further subdivided into B-cell and T-cell types. The low-grade B-cell lymphomas include follicular

lymphoma (FL), B-chronic lymphocytic leukemia (CLL)/small lymphocytic lymphoma (SLL), lymphoplasmacytoid lymphoma and marginal zone lymphoma (MZL). Mantle cell lymphoma (MCL) is an intermediate grade lymphoma. The T-cell group includes T-CLL and mycosis fungoides.

Follicular lymphoma is the most common type of low-grade B-cell lymphoma, and represents 20% of all non-Hodgkin's lymphomas. It is characterized by an indolent clinical course, but with a potential to transform to a more aggressive form of lymphoma. Follicular lymphoma is most often disseminated at diagnosis, and is rarely cured. Although the disease is sensitive to chemotherapy, radiotherapy and immunotherapy, subjects eventually exhaust all options and succumb to progression of disease. The median survival of all subjects with follicular lymphoma is approximately 10 years. The prognosis of follicular lymphoma subjects can be estimated by a constellation of clinical parameters, described as FLIPI (follicular lymphoma international prognostic index), determined at disease presentation. FLIPI includes one "point" for each of: stage III/IV disease; number of nodal sites involved ≥ 5 ; LDH $>$ normal; age ≥ 60 ; and Hb < 12 . Subjects with 0 to 1; 2; or ≥ 3 risk factors belong to good, intermediate and poor-risk groups. The 10-year overall survival is 70%, 51% and 36% for the good, intermediate and poor risk groups, respectively (3).

Because FL, MZL, and MCL are generally incurable, the principal of treatment is palliation. In advanced-stage low-grade lymphoma subjects, the Stanford group showed no advantage in survival between watchful waiting and early intervention.(4) Thus, therapy is instituted only when subjects develop symptoms from their lymphoma. Follicular lymphoma, marginal zone lymphoma and mantle cell lymphoma are sensitive to many treatment modalities, including chemotherapy, radiotherapy and immunotherapy. However, the response is generally not durable and subjects eventually succumb to the disease. Therefore, novel therapies are needed to improve the outcome of subjects with FL, MZL, and MCL.

